1.2.2 Known potential risk

Based on mechanism of action, nonclinical study data, clinical safety data, and the same class drug safety profile of HH2710, hematological toxicity, hepatotoxicity, nephrotoxicity, cardiotoxicity, interstitial lung disease and pancreatic toxicity are assessed as important potential risks.

Hematological toxicity

Hematological parameters changes were observed in 28-day repeat-dose toxicity study of HH2710 in dog. In HH2710 clinical data, the most common Hematological toxicity events were anemia, followed by leukopenia, neutropenia, and thrombocytopenia, and most of the adverse events were CTCAe1/2 grade.

Hepatotoxicity

In 28-day repeat-dose toxicity study of HH2710 in rat, clinical pathology changes at 15 mg/kg/day, 50 mg/kg/day and 150/100 mg/kg/day dose level included increase in ALT, AST in both males and females. In HH2710 clinical data, the common hepatotoxic events were AST, ALT, ALP and GGT increased, and most of the hepatotoxic events were CTCAE grade 1/2.

Nephrotoxicity

In 28-day repeat-dose toxicity study of HH2710 in rat, clinical pathology changes at 50 mg/kg/day dose level on Day 29 included increase in CREA in males, and clinical pathology changes at 150/100 mg/kg/day dose level included increase in CREA in both gender on Day 29. No significant nephrotoxicity was observed in current clinical data.

Cardiotoxicity

The preclinical evidence suggests that following a single dose of HH2710 in conscious beagle dogs at 100 mg/kg, HH2710 could increase HR, decrease PR interval and QT interval without changing the corrected QT (QTcR) in both genders; and also decrease systolic arterial blood pressure (SBP), diastolic arterial blood pressure and mean atrial blood pressure in the males and decrease SBP in the females. The above changes can be recovered within the observation period of 25 hr. No significant cardiotoxicity was observed in current clinical data.

Interstitial lung disease

The preclinical evidence suggests chronic inflammation and alveolar macrophage aggregation in lungs were observed following HH2710 treatment at ≥ 15 mg/kg/day dose level in 28-day repeat-dose toxicity study in rat. Interstitial lung disease cases were observed but causal relationship with study drug could not be figured out.

Pancreatic toxicity

In 28-day repeat-dose toxicity study in SD rats and Beagle dog, pancreas was one of the main target organs. No significant pancreatic toxicity was observed in current clinical data.

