6.3 Dose modifications

6.3.1 Dose modification and dose delay

For patients who do not tolerate the protocol-specified dosing schedule, dose adjustments are permitted in order to allow the patient to continue the study treatment. The following guidelines need to be applied:

These changes must be recorded on the Dosage Administration Record CRF.

All dose modifications should be based on the worst preceding toxicity.

Each patient is only allowed 2 dose reductions as showed in [Table 6-7](#).

If a patient requires a dose interruption of > 14 days from the intended day of the next scheduled dose, then the patient must be discontinued from the study. Patients who discontinue the study for a study related adverse event or an abnormal laboratory value must be followed as described in [Table 6-](#).

Table 6-7 Dose adjustment of HH2710

	HH2710(mg)
Dose	Starting Dose
First dose reduction	75% of the starting dose*
Second dose reduction	50% of the starting dose*

* The actual reduced dose should take into account the drug specification

Adjust reference values in the table below according to the CTCAE V5.0 used in the study.

The criteria for interruption and re-initiation of HH2710 treatment is showed in [Table 6-](#)

Table 6-8 Criteria for interruption, re-initiation of HH2710 treatment and permanently discontinuation

Recommended dose modifications for HH2710	
Worst toxicity	Recommended dose modifications any time during a cycle of therapy, including intended day of dosing^b
CTCAE Grade^a (value)	
No toxicity	Maintain dose level
Investigations (Hematologic)	
Neutropenia (ANC)	
Grade 1 (ANC < LLN - 1500/mm ³)	Maintain dose level
Grade 2 (ANC < 1500 - 1000/mm ³)	Maintain dose level
Grade 3 (ANC < 1000 - 500/mm ³)	Discontinue HH2710: 
 - If elevation lasts for \leq 7 days: Resume treatment at same dose level - If elevation lasts for >7 days: Resume treatment at ≥ 1 dose level
Grade 4 (ANC < 500/mm ³)	Discontinue dose until resolved to \leq Grade 2, then ≥ 1 dose level 
If there is no recovery to \leq Grade 2 or there is recurrent grade 3 or 4 neutropenia, G-CSF/Neulasta may be given at physician discretion.
 
If no recovery to \leq Grade 2, permanently discontinue HH2710

Thrombocytopenia	
Grade 1 (PLT < LLN - 75,000/mm ³)	Maintain dose level
Grade 2 (PLT < 75,000 - 50,000/mm ³)	Maintain dose level

Recommended dose modifications for HH2710	

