Worst toxicity CTCAE Grade^a (value)	Recommended dose modifications any time during a cycle of therapy, including intended day of dosing^b
Grade 3 (PLT < 50,000 - 25,000/mm ³)	
Discontinue dose until resolved to \leq Grade 2, then:
 
 - If resolved in \leq 7 days, then maintain dose level - If resolved in $>$ 7 days, then \downarrow 1 dose level 
If no recovery to \leq Grade 2, permanently discontinue HH2710
 
Second occurrence: discontinue until toxicity resolves to \leq Grade 2, reduce to by another dose level.
 
3rd occurrence permanently discontinue HH2710.

Grade 4 (PLT < 25,000/mm ³)	
Discontinue dose until resolved to \leq Grade 2, then \downarrow 1 dose level
 
If no recovery to \leq Grade 2, permanently discontinue HH2710
 
Second occurrence: discontinue until toxicity resolves to \leq Grade 2, reduce to by another dose level.
 
3rd occurrence permanently discontinue HH2710.

Febrile neutropenia (ANC < 1.0 x 10 ⁹ /L, fever \geq 38.5°C)	Discontinue dose until resolved, then \downarrow 1 dose level
First episode	
Discontinue HH2710 until afebrile and ANC $>$ 1000.
 
Add Filgrastim/Neulasta per physician discretion.

Second episode	
Discontinue HH2710 until afebrile and ANC $>$ 1000.
 
Add Filgrastim/ Neulasta per treating physician discretion.
 
Restart HH2710 at dose reduced by one dose level and monitor as clinically.

Recommended dose modifications for HH2710	
Worst toxicity CTCAE Grade^a (value)	Recommended dose modifications any time during a cycle of therapy, including intended day of dosing^b
Third episode	Discontinue HH2710 until afebrile and ANC >1000. Add Filgrastim/ Neulasta per treating physician discretion. Restart HH2710 reduced by another dose level and monitor as clinically indicated.
Fourth episode	Permanently discontinue HH2710 and continue follow-up protocol.
Investigations (Hematologic) for LCH	Manage as per institutional standard or global guidance.
Investigations (Renal)	
Serum creatinine	
Grade 1 (> ULN - 1.5 x ULN)	Maintain dose level
Grade 2 (>1.5 - 3.0 x baseline; > 1.5 - 3.0 x ULN)	Discontinue dose until resolved to \leq Grade 1 or baseline, then maintain dose level
Grade 3 (>3.0 x baseline; > 3.0 - 6.0 x ULN)	Permanently discontinue HH2710
Grade 4 (> 6.0 x ULN)	Permanently discontinue HH2710
Investigations (Hepatic)*	
Bilirubin	

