Grade 1 (>ULN - 1.5 x ULN if baseline was normal; > 1.0 - 1.5 x baseline if baseline was abnormal)	Maintain dose level

Recommended dose modifications for HH2710	
Worst toxicity CTCAE Grade^a (value)	Recommended dose modifications any time during a cycle of therapy, including intended day of dosing^b
Grade 2 (>1.5 - 3.0 x ULN if baseline was normal; >1.5 - 3.0 x baseline if baseline was abnormal)	Discontinue dose until resolved to \leq Grade 1, then: 
 - If resolved in \leq 7 days, then maintain dose level - If resolved in > 7 days, then \downarrow 1 dose level
Grade 3 (>3.0 - 10.0 x ULN if baseline was normal; >3.0 - 10.0 x baseline if baseline was abnormal)	Discontinue dose until resolved to \leq Grade 1, then: 
 - If resolved in \leq 7 days, then \downarrow 1 dose level - If resolved in > 7 days, then discontinue patient from study drug treatment
Grade 4 (>10.0 x ULN if baseline was normal; >10.0 x baseline if baseline was abnormal)	Permanently discontinue HH2710
AST or ALT	
Grade 1 (>ULN - 3.0 x ULN if baseline was normal; 1.5 - 3.0 x baseline if baseline was abnormal)	Maintain dose level
Grade 2 (>3.0 - 5.0 x ULN if baseline was normal; >3.0 - 5.0 x baseline if baseline was abnormal)	Maintain dose level
Grade 3 (>5.0 - 20.0 x ULN if baseline was normal; >5.0 - 20.0 x baseline if baseline was abnormal)	Discontinue dose until resolved to \leq Grade 1 (or \leq Grade 2 if liver metastases present), then: 
 - If resolved in \leq 7 days, then maintain dose level - If resolved in > 7 days, then \downarrow 1 dose level
Grade 4 (>20.0 x ULN if baseline was normal; >20.0 x baseline if baseline was abnormal)	Permanently discontinue HH2710

Recommended dose modifications for HH2710	
Worst toxicity CTCAE Grade^a (value)	Recommended dose modifications any time during a cycle of therapy, including intended day of dosing^b
ALT/AST > 3 ULN and concomitant TBL > 2 ULN in the absence of evidence of biliary obstruction (i.e., significant elevation of ALP) or some other explanation of the injury (e.g., viral hepatitis, alcohol hepatitis) of any duration (i.e. Hy's law)	Permanently discontinue HH2710
Investigation (metabolic)**	
amylase and/or lipase elevation	
Grade 1 (> ULN - 1.5 x ULN)	Maintain dose level
Grade 2 (>1.5-2.0xULN; >2.0-5.0xULN and asymptomatic)	Maintain dose level

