Grade 3 (>2.0 - 5.0 x ULN with signs or symptoms; >5.0 x ULN and asymptomatic)	Discontinue dose of until resolved to Grade \leq 2, then: 
 - If resolved in \leq 7 days, then maintain dose level - If resolved in > 7 days, then \downarrow 1 dose level
Grade 4 (>5.0 x ULN and with signs or symptoms)	Permanently discontinue HH2710.
Cardiac general	
Grade 1 or 2	Maintain dose level
Grade 3	Discontinue dose until resolved to \leq Grade 1, then \downarrow 1 dose level
Grade 4	Discontinue dose and discontinue patient from study drug treatment

Recommended dose modifications for HH2710	
Worst toxicity CTCAE Grade^a (value)	Recommended dose modifications any time during a cycle of therapy, including intended day of dosing^b
Electrocardiogram QT corrected (QTc) interval prolonged	
Grade 1 or 2 Heart Failure	Maintain dose level
Grade 3 Heart Failure	Permanently discontinue HH2710 and discontinue patient from study drug treatment
Grade 4 Heart Failure	Permanently discontinue HH2710 and discontinue patient from study drug treatment
Grade 2 Ejection Fraction (EF) Decreased (resting EF: 50-40%; or 10-19% drop from baseline)	Discontinue HH2710 until ejection fraction returns to a value greater than the institutional lower limit of normal and the absolute decrease from baseline is $\leq 15\%$, then maintain dose level.
Grade 3-4 EF Decreased (resting EF 39-20%; or $\geq 20\%$ drop from baseline)	Permanently discontinue HH2710
Grade 1 and 2 (QTcF 450-500ms)	Maintain dose level
Grade 3 (QTcF ≥ 501 ms on at least two separate ECGs)	Discontinue dose until resolved to Grade ≤ 2 , then: 
 - If resolved in ≤ 7 days, then maintain dose level - If resolved in > 7 days, then $\downarrow 1$ dose level
Grade 4 (QTcF ≥ 501 ms or > 60 ms change from baseline and Torsades de pointes or polymorphic ventricular tachycardia or signs/symptoms of serious)	Permanently discontinue HH2710
Eye disorders	
Retinal vein occlusion (RVO)	Permanently discontinue HH2710.

Recommended dose modifications for HH2710	
Worst toxicity CTCAE Grade^a (value)	Recommended dose modifications any time during a cycle of therapy, including intended day of dosing^b
Other Grade 1 or 2 eye AEs	Discontinue dose until resolved to baseline, HH2710 could be restarted after assessed by ophthalmologist and investigator, maintain dose level or one dose level reduced as clinically indicated.

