^b If the investigator considers it to be at patient's best interest to resume therapy before the toxicity has resolved to Grade 1 or 2 mentioned above, this may be permitted on a case by case basis, following discussion with Haihe.

* Note: If Grade 3 or 4 hyper-bilirubinemia is due to the indirect (non-conjugated) component only, and hemolysis as the etiology has been ruled out as per institutional guidelines (e.g., review of peripheral blood smear and haptoglobin determination), then \downarrow 1 dose level* and continue treatment at the discretion of the investigator.

**Note: A CT scan or other imaging study to assess the pancreas, liver, and gallbladder must be performed within 1 week of the first occurrence of any \geq Grade 3 of amylase and/or lipase. If asymptomatic Grade 2 elevations of lipase and/or amylase occur again at the reduced dose, patients will be discontinued permanently from study treatment.

***Note: antidiarrheal medication is recommended at the first sign of abdominal cramping, loose stools or overt diarrhea

****Note: This is a general guidance for the other AEs except the above mentioned, and it is recommended that the specialists were involved for special case, and AE must be under adequate treatment before discontinuing.

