6.3.2 Follow-up for toxicities

Patients whose treatment is interrupted or permanently discontinued due to an adverse event or clinically significant laboratory value, must be followed up at least once a week (or more frequently if required by institutional practices, or if clinically indicated) for 4 weeks, and subsequently at approximately 4-week intervals, until resolution or stabilization of the event, whichever comes first.

Appropriate clinical experts such as ophthalmologist, endocrinologist, dermatologist, psychiatrists etc. should be consulted as deemed necessary.

Table 6-9 outlines the follow-up evaluation recommended for toxicities of specific types and CTCAE grades.

Table 6-9 Follow-up evaluations for selected toxicities

TOXICITY	FOLLOW-UP EVALUATION
Blood and lymphatic system disorders	Test twice weekly until \leq CTCAE grade 1, then restart treatment. Continue to test weekly until resolution to baseline or stabilization.
Investigations (hematologic) Neutropenia \geq CTCAE grade 3 Thrombocytopenia \geq CTCAE grade 3	Test twice weekly until \leq CTCAE grade 1, then restart treatment. Continue to test weekly until resolution to baseline or stabilization. Perform physical exam for check on bruising in case of major thrombocytopenia.
Investigations (hepatic) Total bilirubin $\geq 2 \times$ ULN OR AST/ALT \geq CTCAE grade 3 ($> 5 \times$ ULN)	Test twice weekly until \leq CTCAE grade 1, (or \leq CTCAE grade 2 for ALT/AST if liver metastases are present) then restart treatment. Continue to test weekly until resolution to baseline or stabilization. Patients with total bilirubin $>$ ULN (any duration) should have fractionation of bilirubin into total/direct or indirect/direct components and any additional work-up as clinically indicated by these results. Follow-up of hyperbilirubinemia should proceed as per the guidelines above, irrespective of the results of fractionation.
Investigations (metabolic) Amylase or lipase \geq CTCAE grade 3	Test twice weekly until \leq CTCAE grade 2, then restart treatment. Continue to test weekly until resolution to \leq CTCAE grade 1 or stabilization. A CT scan or equivalent imaging procedure to assess the pancreas, liver, and gallbladder is recommended within 7 days of the first occurrence of any \geq

	CTCAE grade 3 result, to exclude disease progression or potential other liver disease. In patients with serum triglycerides \geq 500 mg/dL, urine amylase also needs to be tested.

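### The lipase/amylase recurrence rule in Table 6-8 permanently stops an asymptomatic Grade 2 recurrence but not, as written, a symptomatic Grade 2 or a Grade 3 recurrence

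*Protocol*

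**What the plan says.** All the operative text is in Protocol Section 6.3.1, apart from one line in Section 6.3.2.

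- **Note to the amylase/lipase rows of Table 6-8** (double asterisk, second sentence): "If asymptomatic Grade 2 elevations of lipase and/or amylase occur again at the reduced dose, patients will be discontinued permanently from study treatment".
- **Grade 2 row:** "Grade 2 (>1.5-2.0xULN; >2.0-5.0xULN and asymptomatic"). The action is to maintain the dose. The row has no hold, reduction or recurrence step.
- **Grade 3 row:** "Grade 3 (>2.0 - 5.0 x ULN with signs or symptoms; >5.0 x ULN and asymptomatic"). The drug is held until Grade 2 or lower. It then restarts at the same dose if that took 7 days or less, and one level lower if it took longer. There is no recurrence step.
- **Grade 4 row** (above 5.0 x ULN with signs or symptoms): permanent stop.
- **General caps:** "Each patient is only allowed 2 dose reductions as showed in" Table 6-7, which gives 75% and then 50% of the starting dose. Also: "If a patient requires a dose interruption of > 14 days from the intended day of the next scheduled dose", the patient comes off study.
- **Table 6-9 (Section 6.3.2)**, for amylase or lipase of Grade 3 or worse: test twice weekly until no worse than "CTCAE grade 2, then restart treatment. Continue to test weekly until resolution to" Grade 1 or lower, or stabilization.

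**The concern.** A stopping rule for a monitored toxicity should be at least as strict for a worse event as for a milder one. Here the only recurrence that carries a mandatory stop, short of Grade 4, is the symptom-free Grade 2. A patient whose enzymes rise again with symptoms, or to Grade 3, is governed by rows that keep the drug going or allow a restart. Two sites could act differently on the same laboratory result, depending on whether they follow the words or what they take to be the purpose.

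Section 1.2.2 lists pancreatic toxicity as an important potential risk. The pancreas was a target organ in the 28-day rat and dog studies, and exclusion criterion 22 keeps out patients with a history of pancreatitis or risk factors for it. Lipase and amylase are the monitoring tests for that risk, so their rule should follow severity.

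**Working it through.** No sample size, power or error rate is involved, so the check is to set the texts side by side. I took a recurrence at the reduced dose, at three enzyme levels chosen to fall in the different bands of Table 6-8, and applied the row and the note as written.

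| Recurrence at the reduced dose | Grade in Table 6-8 | Governing text | Action as written |
|---|---|---|---|
| 1.8 x ULN, no symptoms | 2 | Note | Permanent stop |
| 3 x ULN, no symptoms | 2 | Note | Permanent stop |
| 1.8 x ULN, with symptoms | 2 | Grade 2 row | Dose maintained |
| 3 x ULN, with symptoms | 3 | Grade 3 row | Hold, then restart |
| 6 x ULN, no symptoms | 3 | Grade 3 row | Hold, then restart |
| 6 x ULN, with symptoms | 4 | Grade 4 row | Permanent stop |

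At a fixed level of 1.8 or 3 x ULN, adding symptoms turns a mandatory stop into continued dosing or a restart. Without symptoms, going from 3 to 6 x ULN does the same.

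**Do the general rules supply the missing stop for Grade 3?** Only in part. Take residual Grade 2 at restart as not being a recurrence.

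- Recurrence at the first reduced dose (75%): recovery in 7 days or less allows restart at 75%; in 8-14 days, restart at 50%; beyond 14 days, off study.
- Recurrence at the second reduced dose (50%): recovery in 7 days or less allows restart at 50%. In 8-14 days the row calls for a reduction, but both have been used and the text gives no action. Beyond 14 days, off study.

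The other general provisions do not close the gap. The instruction to base dose modifications on the worst preceding toxicity selects the row for the worst grade; for Grade 3 that row is hold and restart. Footnote b allows an earlier restart, case by case, after discussion with the sponsor. Section 7.1.4.2 lets the investigator withdraw a patient for an intolerable event or a clinically significant laboratory value, but that is a judgement, whereas the note is mandatory.

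**Does the note fit its rows?** In two respects it does not.

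1. It speaks of recurrence at the reduced dose, but asymptomatic Grade 2 never leads to a reduction. Among the enzyme rows only Grade 3 lasting more than 7 days does.
2. The Grade 3 row and Table 6-9 both allow restart at Grade 2. If residual asymptomatic Grade 2 counted as occurring again, a permitted restart at the reduced dose would at once be a permanent stop. The note does not say whether it counts.

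**Comparison within Table 6-8.** The thrombocytopenia Grade 3 and Grade 4 rows both spell out what happens on recurrence, ending with "3rd occurrence permanently discontinue HH2710", while Grade 2 thrombocytopenia is maintained. There the recurrence stop sits with the severe grades.

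**The case against.** The strongest reply is that any sensible investigator would apply the note all the more to Grade 3, and that the worst-toxicity instruction points the same way. That is a fair guess at the intent, but the text does not say it. The first sentence of the same note refers to any event of Grade 3 or higher, so the second could have done so too.

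A second reply is that a Grade 3 row without a recurrence stop is common in this table: AST/ALT, QTc, hypertension and diarrhea have none. That stands. It makes the note the outlier and limits what the thrombocytopenia comparison can show.

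It also leads to a tempting inference, that Grade 2 in the note is simply a slip for Grade 3. The documents do not support that. The mismatch with the Grade 2 row makes it possible, but nothing shows which threshold was meant.

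The third reply concerns size, and it stands. Symptomatic Grade 2 is only the band >1.5-2.0 x ULN. Grade 4 enzyme elevations and Grade 3 or worse pancreatitis are already permanent stops. Section 1.2.2 says: "No significant pancreatic toxicity was observed in current clinical data". SAP Section 7 states that the program is stopped and the study terminated early.

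**Conclusion.** The point holds as a defect of wording in a safety rule. As written, the milder recurrence carries the harsher mandatory action, and the note does not match the rows it qualifies. This rests on a literal reading of Table 6-8. The inversion does not depend on how residual Grade 2 is treated: if it did count as a recurrence, some Grade 3 patients would be stopped after restart, but because of the residual Grade 2 and not because of the Grade 3 event.

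A reader might go further and infer that the protocol requires Grade 3 recurrences to stay on drug, or that the trial's results are compromised. Neither follows. The two caps and investigator withdrawal can still end treatment. The DLT criteria in Table 6-6 are separate from this note, and no DLT, MTD or ORR result changes. The documents give no frequency for such recurrences, so no rate of affected patients can be stated.

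The priority is minor. The benefit is for any patient still on treatment, and for any later protocol that reuses the table.

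**What to change.** Replace the second sentence of the note with wording such as:

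*Any lipase and/or amylase elevation of Grade 2 or higher, with or without symptoms, that recurs at the reduced dose leads to permanent discontinuation of HH2710. Residual asymptomatic Grade 2 at a restart that this table permits does not by itself count as a recurrence; worsening to Grade 3 or higher, or new symptoms, after such a restart does.*

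The safety physician and the SMC should confirm whether the asymptomatic Grade 2 threshold was intended. Whichever threshold they keep, the stop must also apply to every more severe recurrence. They should also say how long residual Grade 2 may persist after a restart. Otherwise a patient who never clears it could continue, while one who recovers to Grade 1 and returns to Grade 2 must stop.

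The cost is one written amendment under Section 12.1, with sponsor, IRB/IEC/REB and, where required, health authority approval. It adds no patients or procedures. The downside is that a few patients with recurrent Grade 3 or symptomatic Grade 2 elevations would stop the drug earlier than the present text requires.
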